8.1.1 Definition of a Serious Adverse Event

An SAE is any untoward medical occurrence occurring at any dose that results in any of the following outcomes:

- Results in death
- Is life-threatening (defined as an event in which the subject was at risk of death at the time of the event; it does not refer to an event which hypothetically might have caused death if it were more severe)
- Requires inpatient hospitalization or prolongation of existing hospitalization
- Results in persistent or significant disability/incapacity
- Is a congenital anomaly/birth defect
- Is an important medical event (defined as a medical event(s) that may not be immediately life-threatening or result in death or hospitalization but, based upon appropriate medical and scientific judgment may jeopardize the patient/subject or may require medical or surgical intervention to prevent one of the other serious outcomes listed in the definition above). Examples of such events include but are not limited to: allergic bronchospasm requiring intensive treatment in an emergency room or at home; blood dyscrasia or convulsions that do not result in inpatient hospitalization; the development of drug dependency or drug abuse.

Treatment on an outpatient emergency basis that does not result in hospital admission, or a hospitalization that is elective or is a preplanned treatment for a pre-existing condition that has not worsened since the start of the study, is not considered an SAE.

8.2 Severity of Adverse Events

The severity of an AE will be determined by the investigator according to the following definitions:

- **Mild:** Awareness of event, but easily tolerated and does not disrupt usual activity
- **Moderate:** Discomfort sufficient to cause interference with usual activity
- **Severe:** Incapacitating, with inability to perform usual activities

8.3 Relationship of Adverse Events to Study Drug

The relationship of AEs to the study drug will be assessed by the investigator according to the following definitions:

- **Not suspected:** The temporal relationship of the event to the study drug makes a causal relationship unlikely, or, other drugs, therapeutic interventions or underlying conditions provide a sufficient explanation for the observed event.
- **Suspected:** The temporal relationship of the event to the study drug makes a causal relationship possible or other drugs, therapeutic interventions or underlying conditions do not provide a sufficient explanation for the observed event.

If there is any valid reason, even if undetermined, for suspecting a possible cause-and-effect relationship between the study drug and the occurrence of the AE, then the AE should be considered “suspected.”

If the relationship between the AE and the study drug is determined by the sponsor to be “suspected,” the event will be considered to be related to the study drug for the purposes of expedited regulatory reporting.

8.4 Documentation of Adverse Events

All AEs must be completely recorded on the Adverse Events section of the eCRF. The collection of AE information will begin after the subject has signed informed consent and continue up through the Test of Cure Visit (Randomization Period) or up through the End of Treatment Visit (Optional Open-label Extension or Enrollment B). Subjects experiencing AEs that cause interruption or discontinuation of study drug, or those experiencing AEs that are present at the end of their participation in the study or that resulted in permanent discontinuation will receive follow-up as appropriate until the AEs have either resolved or have stabilized.

For each AE, the Investigator will evaluate and report the following:

- Onset (date);
- Resolution (date);
- Severity grade (mild, moderate, severe);
- Relationship to study drug (not suspected, suspected);
- Action taken (none, study drug temporarily interrupted, study drug permanently discontinued, concomitant medication taken, hospitalization/prolonged hospitalization, other);
- Serious (yes/no);
- Whether the AE occurred at the study drug application site (yes/no);

- For AEs of the ear, which ear (left, right, or both) was affected.

8.4.1 Additional Reporting Requirements for Serious Adverse Events

All SAEs that occur from the time the subject has signed the informed consent until the Test of Cure Visit (Randomization Period) or up through the End of Treatment Visit (Optional Open-label Extension or Enrollment B) will be reported. Additionally, any SAEs “suspected” to be related to the study drug and discovered by the investigator at any time after the study should be reported. Each of these SAEs must be reported to the sponsor’s designee within 24 hours of the occurrence of the SAE, or within 24 hours of learning of the SAE. Information on recurrent episodes, complications, or progression of the initial SAE must also be reported within 24 hours of the investigator receiving the information.

Reporting may be by telephone, confirmed facsimile transmission, or confirmed email to the medical monitor. The investigator must assess the relationship of the SAE to study drug and must complete the SAE form. If only limited information is initially available, follow-up reports are required. Follow-up information (e.g., discharge summary) will be retained in the subject’s chart and a copy (with the subject’s personal information removed and with the subject identified only by subject number) will be sent by confirmed facsimile transmission or confirmed email to the medical monitor. In the event of death, if an autopsy is performed, a copy of the report (with the subject’s personal information removed and with the subject identified only by subject number) should be sent to the medical monitor.

As required and after the sponsor’s review and determination of causality, the sponsor and/or designee will notify investigators of all AEs that are serious, unexpected, and considered by the investigator to have a suspected relationship to the study drug. This notification will be in the form of an update to the Investigator’s Brochure (i.e., “15-day letter”). An AE, whether serious or non-serious, is designated unexpected (unlabeled) if it is not reported in the clinical safety section of the Investigator’s Brochure or if the event is of greater frequency, specificity or severity.

Upon receiving such notices, the investigator must review and retain the notice with the Investigator’s Brochure and immediately submit a copy of this information to the responsible IRB according to local regulations. The investigator and IRB will determine if the informed consent requires revision. The investigator should also comply with the IRB procedures for reporting any other safety information. Follow-up reports should be submitted when requested or when pertinent information becomes available.

The sponsor will report all SAEs to the US FDA on the appropriate schedule depending on the event’s expectedness and relationship to study drug based on the available information as presented in the Investigator’s Brochure.

Any SAE occurring after the final study visit and which is not considered to be of “suspected” relationship to study drug does not need to be reported.

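### For serious, unexpected adverse events, Section 8.3 ties expedited reporting to the sponsor's causality call but Section 8.4.1 ties the required notice to sites to the investigator's

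*Combined protocol and SAP*

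**What the plan says.** Section 8.3 gives the first causality assessment to the site: "The relationship of AEs to the study drug will be assessed by the investigator according to the following definitions". It then gives the sponsor's judgement an effect of its own. When the sponsor rates the relationship as suspected, the section says that "the event will be considered to be related to the study drug for the purposes of expedited regulatory reporting".

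Section 8.4.1 sets the rule for informing sites. The notice comes once the sponsor has made its own causality determination, and it must cover every adverse event that is serious, unexpected and "considered by the investigator to have a suspected relationship to the study drug". It goes out as an Investigator's Brochure update, also called a 15-day letter. The investigator who receives it keeps it with the Brochure and passes a copy to the IRB. Section 8.4.1 adds: "The investigator and IRB will determine if the informed consent requires revision".

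On the regulator, Section 8.4.1 says: "The sponsor will report all SAEs to the US FDA on the appropriate schedule depending on" expectedness and relationship. It does not say whose view of relationship governs.

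**The concern.** Two linked safety outputs, expedited reporting and the notice to sites, rest on two different assessors. The Section 8.4.1 sentence is also at odds with itself: it waits for the sponsor's causality determination and then gives that determination no part in the criterion.

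The events left out are those where only the sponsor suspects the drug. The sponsor receives serious events from up to 20 sites (Section 3.5) and may see a pattern that no single site can. Site notices let other investigators, and through them the IRBs, consider whether current subjects need new information. If the notice is not required, neither are those later steps.

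**Working it through.** No formula applies. The check sets the rules side by side for one adverse event that is both serious and unexpected, and works through the four combinations of causality judgement.

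| Investigator | Sponsor | Treated as related for expedited reporting (8.3) | Notice to sites required (8.4.1) |
|---|---|---|---|
| Suspected | Suspected | Yes | Yes |
| Not suspected | Suspected | Yes | **No** |
| Suspected | Not suspected | Not by the 8.3 sentence | Yes |
| Not suspected | Not suspected | No | No |

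Row 2 is the gap. Row 3 is the mismatch in the other direction, and it matters for the choice of fix. In all four rows FDA receives the event, because Section 8.4.1 sends every SAE to FDA and lets only the schedule vary. No other section extends the required notice to events suspected by the sponsor alone.

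**Can row 2 occur?** The Section 8.3 definitions overlap. Take an event whose timing makes a drug effect possible but which also has a sufficient alternative explanation. It meets the second limb of the not-suspected definition and the first limb of the suspected definition. A further sentence in Section 8.3 says that any valid reason for suspicion should lead to a suspected rating. That narrows the overlap but still calls for judgement, so two assessors can differ in good faith.

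**Who is covered?**
- Subjects expected to receive miconazole oil, from the Section 3.4.2 assumptions: 110 randomized to active + 55 vehicle subjects entering the extension + 170 in Enrollment B = 335. The figure of 300 in the protocol is the target for 14-day exposure evaluable for safety, not the number exposed.
- All subjects under the rule: Section 8.1 counts the comparator as study drug, so the rule covers the planned 220 + 170 = 390 (Section 3.4).

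**How often?** This cannot be derived. Section 1.1 reports no SAEs in Phase 2, and the documents give no rate of disagreement between sponsor and investigator.

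**The case against.** The best defence is that the sentence already gives the sponsor a role. It opens by saying that notices go out as required and after the sponsor has determined causality, and it calls the notice a 15-day letter. On that reading the notice simply follows the expedited-reporting decision in Section 8.3, and the reference to the investigator is loose drafting. This may well be what was intended. But the protocol does not say what the opening words refer to or what triggers a 15-day letter, and the operative criterion still names the investigator. The defence is therefore a reason to correct the wording.

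Three limits stand:
- Section 8.4.1 states a class of events that must be notified. It does not say that only these may be. A reader might infer that sponsor-suspected events would not reach sites, but the text supports only that notice of them is not required.
- The affected events must be unexpected as well as serious. A reader might take the gap to cover serious related events in general; it does not.
- The low threshold for a suspected rating in Section 8.3 makes suspicion by the sponsor alone less likely, though not impossible.

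**Conclusion.** The inconsistency is real, and the notification rule is wrong as written, though the point is minor. For a serious, unexpected event suspected by the sponsor but not by the investigator, Section 8.3 treats the event as related for expedited reporting, while Section 8.4.1 requires no notice to sites and so starts no IRB submission or consent review. This rests on reading the Section 8.4.1 criterion literally.

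A reader might also infer that the regulator would miss such events or that the sponsor means to withhold notices. The documents support neither. All SAEs go to FDA, and the opening of the sentence suggests that the sponsor's view was meant to count.

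The practical size is unknown and probably a handful of events at most. The endpoint, sample size, error control and efficacy analyses are untouched.

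**What to change.** In Section 8.4.1, replace *considered by the investigator* with *considered by the sponsor or the investigator* in the criterion for notifying investigators. Row 2 of the table then becomes a required notice, rows 1 and 3 keep theirs, and every serious, unexpected event treated as related under Section 8.3 also reaches the sites.

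Do not substitute the sponsor alone. That would match Section 8.3 word for word but would remove the row 3 notices, for events suspected only by the investigator, which the present text requires.

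The cost is one phrase in a protocol amendment and at most a few more notices for sites and IRBs to handle. No assessment, visit, treatment rule or analysis changes.

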8.5 Pregnancy

Females of childbearing potential, as defined in Section 4.1.1 (Enrollment A) and Section 4.2.1 (Enrollment B), must use an effective method of contraception from screening up through the final study visit. Acceptable methods include the use of at least one of the following: 1) IUD; 2) hormonal contraceptives (oral, injectable, implant, or ring); 3) barrier contraceptives (condom or diaphragm) with spermicide; or 4) abstinence.

Should a pregnancy occur, it must be reported and recorded on the pregnancy form and sent by confirmed facsimile or confirmed email to the medical monitor, as well as documented in the eCRF. Pregnancy in itself is not regarded as an AE unless there is a suspicion that the study drug product may have interfered with the effectiveness of a contraceptive medication.

In the event of pregnancy that is detected during treatment with study drug, the subject must be withdrawn from further treatment with study drug. The subject may continue to participate in the study on a case-by-case basis after discussion between the investigator and the sponsor and/or the sponsor's designee.

The outcome of all pregnancies (spontaneous miscarriage, elective termination, normal birth, or congenital abnormality) must be followed up and documented even if the subject was discontinued from the study and/or study drug.

8.6 Study Contacts

Study contacts will be provided in a separate document.

9 STUDY TREATMENTS

9.1 Description of Study Drug

Miconazole oil contains the active ingredient, 2% miconazole, formulated in an oil vehicle containing refined peanut oil, light mineral oil, oleth-2, and isopropyl myristate. For subjects randomized to the vehicle oil group, the vehicle oil will not contain miconazole and will instead contain a greater amount of refined peanut oil and mineral oil to account for the absence of the miconazole.

Study drug will be supplied in bottles containing ~20 grams of product. The dispensing tip will deliver approximately 30 mg of product per drop.

9.1.1 Administration

Subjects will be seated or lying on one side with the head positioned so the ear being treated is facing up. If both ears are being treated, the ear that appears to have less severe disease will be treated first. The subject or caregiver will gently pull the ear lobe backward and upward and apply 5 drops of study drug into the ear. The subject will be instructed to keep the head positioned with the ear facing up for approximately 3 to 5 minutes to allow the study drug to coat the ear canal. After this time, the subject can then straighten his/her head, and excess material dripping out of the ear can be gently patted using a clean cotton ball.

If both ears are being treated, the subject will then wait at least 5 minutes, then repeat this procedure for the second ear.

During the Randomization Period, while on study treatment, subjects will be instructed to avoid getting water in the ear, to consider drying excessive water in the ear by using a blow dryer, and to place a Vaseline-impregnated cotton ball over the affected ear(s) to help keep water out of the ear(s) while bathing or showering. Subjects in the Optional Open-label Extension and subjects in Enrollment B who have signs and/or symptoms of otomycosis may also be given these instructions.

Subjects in both portions will be asked to avoid bathing or showering for at least 30 minutes after applying study drug.

9.2 Randomization

For the Randomization Period, subjects will be randomized in a 1:1 ratio to one of two groups: 1) 14-day treatment with miconazole oil; or 2) 14-day treatment with miconazole oil vehicle. Randomization is not applicable to either the Optional Open-label Extension of Enrollment A or to Enrollment B.

9.3 Blinding/Unblinding

The contents of the study drug (miconazole oil versus vehicle) will be blinded to both the investigator (and all study staff) and the subject during the Randomization Period of Enrollment A. Randomized study drug will be packaged in identical bottles and will be labeled with a randomization number rather than the contents of the bottle.

If it becomes necessary to unblind a subject's treatment assignment in case of emergency, the investigator should contact the sponsor. A person at the sponsor organization who is not otherwise involved with the study will maintain a randomization list that will enable that person to inform the investigator of the subject's treatment allocation. The treatment allocation is to be obtained only if a medical emergency exists and knowledge of the medication being taken will influence the medical management of the subject.

9.4 Study Drug Handling and Dispensing

9.4.1 Packaging and Labeling

The miconazole oil and the oil vehicle will be manufactured, packaged and labeled by Hill Dermaceuticals, Inc. It will be packaged in dropper bottles, each of which will contain ~20 grams of study drug. The dropper will dispense approximately 30 mg per drop.

For the Randomization Period of Enrollment A, the study drug and vehicle will be packaged in primary bottle and provided in identical study drug kits. Each kit will contain the investigational drug product (or placebo product), reserve identical drug product (or placebo product), bag of cotton balls, and Vaseline jelly. The subject will be dispensed the kit (minus the reserve product) at Baseline only. The dropper bottles will be weighed with the cap on prior to dispensing. If the

subject loses a bottle (lost or damaged), the reserve bottle will be dispensed using a replacement process as defined in the randomization plan.

For the Optional Open-label Extension of Enrollment A and for Enrollment B, the study drug will be packaged in a primary bottle that will be dispensed directly to the subject. The dropper bottles will be weighed with the cap on prior to dispensing. If the subject loses a bottle (lost or damaged), a reserve bottle will be dispensed from the study drug inventory packaged for open-label use.

Each drug kit dispensed will be documented on the drug accountability log.

Labels on the drug kit will contain the following information:

- Protocol number
- Subject number
- Space for entry of the subject initials
- Space for entry of date dispensed
- A statement reading, “For otic use only. Avoid contact with eyes and lips”
- A statement reading, “Store at controlled room temperature 20°C to 25°C (68°F to 77°F) with excursions permitted between 15°C to 30°C (59°F to 86°F)”
- A statement indicating the sponsor, Hill Dermaceuticals
- A statement indicating the quantity of product (20 grams)
- A statement reading, “Caution: New Drug - Limited by Federal Law to Investigational Use”
- A statement reading, “Keep out of Reach of Children”

9.4.2 Storage

The study drug is to be stored at room temperature (20°C to 25°C, or 68°F to 77°F), with excursions permitted between 15°C and 30°C (59°F and 86°F). All investigational study drug must be stored in a secure facility, with access limited to the investigator and authorized staff.

9.5 Accountability

The investigator or designee (e.g, study coordinator or pharmacist) is responsible for ensuring storage as per the label on the study drug and adequate accountability of all used and unused study drug. Adequate accountability includes acknowledgment of receipt of each shipment of study drug (quantity and condition), records of administration (including container number, date administered, subject number, and the initials of the person administering the drug), and documentation of quantities returned to the sponsor (or designee).

At time points during the course of the study and/or upon completion of the study, the sponsor or designee will review and verify the investigator's accountability records.

9.6 Return and Destruction

At the completion of the study, following verification of the investigator's accountability records by the sponsor and/or designee, all study drug must be returned to the sponsor or designee. This would include study drug returned by the subjects at the completion of the study, and reserve products that were not used.

10 STATISTICAL CONSIDERATIONS

All statistical processing will be performed using Statistical Analysis System (SAS[®]) Version 9.4 or higher. Except where noted, all statistical tests will be two-sided and will be performed at the 0.05 level of significance.

Descriptive statistics will be used to provide an overview of the efficacy and safety results. For categorical parameters, the number and percentage of subjects in each category will be presented. For continuous parameters, descriptive statistics will include n (number of subjects), mean, and standard deviation, median, minimum, and maximum.

Full details of statistical analyses will be provided in a separate statistical analysis plan.

10.1 Study Endpoints

10.1.1 Primary Efficacy Endpoint

The primary efficacy endpoint will be the percentage of subjects at the Test of Cure Visit with "therapeutic cure", defined as "mycological cure" plus "clinical cure" for the study ear, at the end of the Randomization Period for each subject. Mycological cure is defined as a negative mycological culture, and clinical cure is defined as the absence of all otomycosis signs and symptoms based on investigator assessment according to the scales for each individual sign or symptom. See Section 7.4 for the scales for each otomycosis sign and symptom.

10.1.2 Secondary Efficacy Endpoints

Secondary efficacy endpoints will include the following (each having been assessed at the end of the Randomization Period for each subject):

- Percentage of subjects with mycological cure at the Test of Cure Visit.
- Percentage of subjects with clinical cure at the Test of Cure Visit.

10.1.3 Tertiary Efficacy Endpoints

Tertiary efficacy endpoints will include the following (each having been assessed at the end of the Randomization Period for each subject):

- Percentage of subjects with "modified therapeutic cure" at the Test of Cure Visit, defined as mycological cure plus a score of 0 for the clinical sign of fungal elements plus a score of 0 or 1 for each of the clinical signs and symptoms of pruritus, debris, and aural fullness.

- Percentage of subjects with “therapeutic improvement” at the Test of Cure Visit, defined as mycological cure plus a score of 0 or 1 for each of the clinical signs and symptoms of fungal elements, pruritus, debris, and aural fullness.

